### **11.2 Information management and analysis software**

CAPRISA uses the DataFax system to store data electronically. The current version of DataFax use is Version 4.1

Statistical Analysis Software (SAS) is used for analysis purposes. The current version in use is version 9.3.

### **11.3 Data entry, editing and management, including handling of data collection forms, different versions of data**

Instructions concerning the recording of study data on CRFs will be provided by the CAPRISA Data Management core. Completed CRFs must be checked by the designated on-site Quality Control officer and upon approval, must be submitted via fax into the DataFax system. CAPRISA Data encoders and Data Managers located at the Nelson R. Mandela School of Medicine verify and validate the patient data. Quality control reports are produced, and approved data then added to the study database according to CAPRISA data management (SOPs) Study Operating Procedures.

It is the responsibility of the CAPRISA data management core to assure the quality of computerized data for the study. Study staff will be trained in source documentation requirements in accordance with the CAP011 SOP for Source Documentation and in proper forms completion techniques.

Database files will be password-protected, and access to the files will be limited to authorized study staff members only. Quality control and validation checks will be performed and data cleaning steps will be undertaken prior to finalizing the study database for analysis. Analyses will be conducted by study statisticians.

#### **11.4 Data Storage**

Original and DataFax electronic copies of study CRFs and related documents will be stored securely both during and after study completion. During the study, the original completed forms for each participant will be kept on-site at the CAPRISA eThekweni CRS. The forms will be stored in an access secured, double-locked, fire and waterproof room. Upon completion of the study, and finalization of the database for analysis, the original forms will be bound and kept off-site (separate site) for long-term storage. CAPRISA has a standing agreement with Metrofile to archive large amounts of documents. CRF data on the DataFax server will be accessible to the study staff and the statistician in a read-only mode. The data management team will have write-access, with access being restricted by passwords and validation levels. Study staff that has access to the data on the computer systems will be trained in how to access the system and the importance of system security. All information will be backed-up at regular intervals, and backups will be stored in file cabinets or secure areas with limited access

#### **11.5 Quality control/assurance**

A quality check of the study forms will be conducted before the forms are data faxed. The QC procedures will specify the following types of checks:

- There are no illegible handwritten items, spelling errors, etc.
- Responses are clearly within designated spaces.
- All fields are completed with participant data or reason for no data is noted in or near the field.
- The participant's PID is recorded on all pages of the forms.
- The CAPRISA laboratory manager will also be responsible for checking that all the laboratories involved in the study are complying with QA procedures. The CAPRISA pharmacist will check that all drug related documentation meets Good Clinical Practice (GCP) requirements for drug accountability.

QA/QC of data will be undertaken according to the SOPs.

## **12.0 BIOHAZARD CONTAINMENT**

As the transmission of HIV and other pathogens can occur through contact with contaminated needles, blood, blood products, and other secretions, appropriate blood and secretion precautions will be employed by all personnel in the drawing of blood and collection of other specimens and shipping and handling of all specimens for this study, as currently recommended by the Centers for Disease Control and Prevention and the National Institutes of Health.

All dangerous materials, including diagnostic specimens and infectious substances, must be transported using packaging mandated by CFR 42 Part 72. Please refer to instructions detailed in the International Air Transport Association (IATA) Dangerous Goods Regulations.

## Modifications to Statistical Analysis Plan after Trial Initiation

| Version | Date            | Changes from previous version   |
|---------|-----------------|---|
| 1       | 7 August 2017   |   |
| 2       | 2 November 2018 | 

- Addition of signature for statistician

- Use of Fisher's exact test as an alternative to Chi-square test in section 6

- Move mention of log binomial/Poisson regression from 6.6 to 6.3

- Addition of use of the Gehan-Breslow-Wilcoxon test to 6.4

 |

## 1. STUDY OBJECTIVES

### 1.1. Primary Objective

To determine if a Moxifloxacin-containing regimen, [Isoniazid (H), Rifampicin (R), Pyrazinamide (Z), Moxifloxacin (M)] of 24 weeks duration is superior to a control regimen [Isoniazid (H), Rifampicin(R), Pyrazinamide (Z), Ethambutol (E)] of 24 weeks duration in improving treatment outcomes in patients with recurrent TB.

### 1.2. Secondary Objectives

1. To determine the time to culture-conversion of the Moxifloxacin regimen and the Ethambutol regimen using data from 2-, 4-, 6-, and 8-week cultures
2. To compare the proportion of patients with any Grade 3 or 4 adverse reactions
3. To compare adverse events and 2-month culture conversion rates among HIV-infected patients vs. HIV-uninfected patients between the study arms
4. To compare the rates of treatment failure and recurrence of the intervention and control arm.
5. To compare TB cure rates at month 6 and at end of TB treatment between the intervention and control arm.

## 2. STUDY DESIGN

This is an open label randomized controlled clinical trial comparing two regimens for treatment of smear-positive pulmonary TB, among patients previously treated for TB. The primary objective is to determine if a Moxifloxacin-containing regimen, substituting Moxifloxacin for Ethambutol, of 24 weeks duration is superior to a control regimen of 24 weeks duration in improving treatment outcomes in patients with recurrent TB.

This study will include adults 18 years and over with a previous history of TB. HIV infected and uninfected patients will be included in the study as well as patients on ARVs provided that these are not contra-indicated with any of the study drugs. Patients with M tuberculosis

resistance to Rifampicin will be excluded at screening using Gene Xpert technology. A maximum of 330 participants will be included in the study.

Patients will be randomized in a 1:1 ratio to receive one of the two TB retreatment regimens, as outlined in the table below.

|                         | Intensive Phase (2 months) | Continuation Phase |
|-------------------------|-----------------------------------|---------------------------|
| Intervention Arm | HRZM* daily (2 months)            | HRM* daily (4 months)     |
| Control Arm      | HRZE* daily (2 months)            | HR* daily (4 months)      |

\* Isoniazid (H), Rifampicin (R), Pyrazinamide (Z), Moxifloxacin (M), Ethambutol (E)

The duration of TB treatment may increase due to a delay in the time to sputum conversion which will result in the extension of TB treatment beyond 6 months. Following treatment, participants will be followed up on a two-monthly basis for 12 months.

### 3. INTERIM DATA ANALYSIS AND DATA MONITORING

The CAPRISA SOP on DSMB preparations (SOP # CA STA 06) will be used to ensure that the quality of the data being used for this report is of high and reliable quality.

Interim results will include a summary of screening and enrolment, a summary of status for all enrolled participants (completed, discontinued early, possibly lost to follow-up, or continuing), retention rates, descriptive statistics of baseline variables (demographic, recent medical history), protocol violations (including both violations at enrollment/randomisation and violations after enrolment) and adverse events (including serious adverse events).

Data management quality indicators such as the total number of datafax CRF pages received, total number of QC notes placed on data received, QC rate per 100 pages, percent QC resolved, and number of days to QC resolution will be given.

For the safety data, adverse events occurring during the study will be summarised in frequency tables by study arm. Adverse events will be coded using the MedDRA system, version 15 or higher. Safety data will be summarised for all study participants who were consented, enrolled, and randomised to study arm, excluding those participants who never provided any safety data after enrollment.

No formal stopping rules are set. The Safety Monitoring Committee (SMC) should review all available safety data to determine whether there are any safety concerns and whether early termination of the study is warranted. There are circumstances in which some interpretation or flexibility may be required. If some indication of harm is found the DSMB should strongly consider taking action.

#### **4. ANALYSIS POPULATION DEFINITIONS**

All primary and most secondary analysis will be conducted based on the intention-to-treat (ITT) principle. However, for purposes of assessing the effectiveness of the implementation model, various analysis populations are defined as follows:

##### Intention-to-treat population

This population consists of all participants enrolled and randomised to the intervention and control arms. Individuals who will be identified as ineligible for enrolment based on criteria pre-randomisation criteria will be excluded. Moreover, individuals with no post-randomisation visit and no data collected will be excluded.

##### Per protocol Population

This is a subset of the ITT population, excluding all subsequent data collected from participants with a documented interruption of TB treatment for three or more consecutive months arising from:

- Missed visits,
- An adverse event

## 5. GENERAL STATISTICAL ISSUES

All tests will be two-sided, and the significance level will be 0.05.

Outliers will be identified by looking at summary statistics and scatter plots. All outliers detected will be verified from the source documentation. Outliers that have biologically impossible values will be excluded from all data summaries and analyses. If one (or several) outlier(s) change(s) the interpretation of the data substantially, two summaries and analyses will be done, one with and one without the outlier(s).

If a participant has missing data at a specific time point, data at all non-missing time points for the participant will be used and included in the summaries. Missing data will be ignored (i.e. treated as missing at random) unless patterns are identified which would potentially bias analysis results.

Where applicable, analyses will be stratified by HIV status.

All statistical analyses will be done using SAS (SAS Institute Inc., Cary) version 9.4 or higher.

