## **9.0 STATISTICAL CONSIDERATIONS**

### **9.1 Sample size determination:**

A total of 330 patients will be enrolled. A two group continuity corrected chi square test with a 0.05 two-sided significance level will have 80% power to detect the difference between 75% of patients having culture conversion in the Intervention arm and 60% of patients having culture conversion in the Control arm. A previous unpublished retrospective review at the study site comparing the treatment outcome in retreatment

patients with TB using the standard 4 drug regimen, showed a cure and completion rate of 60.1%. According to WHO surveillance data, the retreatment regimen is successful in about 70% of patients, and other retrospective studies show treatment success rates of 26 – 92%. Thus, 75% is a realistic cure and completion rate to aim for in the Intervention group. A previous unpublished retrospective review at the study site comparing the treatment outcome in retreatment patients with TB using the standard 4 drug regimen, showed a cure and completion rate of 60.1%. According to WHO surveillance data, the retreatment regimen is successful in about 70% of patients, and other retrospective studies show treatment success rates of 26 – 92%. Thus, 75% is a realistic cure and completion rate to aim for in the Intervention group.

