## **9.2 Analysis including statistical methods**

To answer the primary objective of this study the sputum culture conversion rates at the end of the intensive phase and at month 6 will be compared between the two treatment arms. This will be done by calculating the proportion of culture conversions in each of the two arms and comparing these using the chi-square test.

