## 6.3. Primary objective

*To determine if a Moxifloxacin-containing regimen, [Isoniazid (H), Rifampicin (R), Pyrazinamide (Z), Moxifloxacin (M)] of 24 weeks duration is superior to a control regimen [Isoniazid (H), Rifampicin(R), Pyrazinamide (Z), Ethambutol (E)] of 24 weeks duration in improving treatment outcomes in patients with recurrent TB.*

To answer the primary objective of this study the culture conversion rates will be compared between the two treatment arms at the end of the intensive phase and at month 6, where culture conversion is defined as the first of two negative (or no growth) cultures at two different visits without an intervening positive culture. This will be done by calculating the proportion of culture conversions in each of the two arms and at each of the two time points and comparing these using the chi-square test or Fisher's exact test. Log binomial regression

or Poisson regression with robust variance will also be used to improve precision of the treatment effect estimates.

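### The one primary objective is tested at two time points, each at 0.05, with no rule for what counts as success; the sample size covers one contrast at an unnamed time point

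*SAP*

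**What the plan says.** SAP 6.3 restates one primary objective, superiority of the moxifloxacin regimen in treatment outcomes. It answers it by comparing the proportion converted "at each of the two time points and comparing these using the chi-square test" or Fisher's exact test. It adds that log binomial "or Poisson regression with robust variance will also be used to improve precision" of the effect estimates. Protocol 9.2 has the same two comparisons ("sputum culture conversion rates at the end of the intensive phase and at month 6 will be compared between the two treatment arms") and names only the chi-square test.

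SAP 5 applies to all of this: "All tests will be two-sided, and the significance level will be 0.05". It also says "Where applicable, analyses will be stratified by HIV status".

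Protocol 9.1 plans with "A two group continuity corrected chi square test with a 0.05 two-sided significance level", giving "80% power to detect the difference between 75% of patients having culture conversion in the Intervention arm" against 60% in the Control arm. No time point is attached to these rates. The 60% is supported by a retrospective review at the site that "showed a cure and completion rate of 60.1" per cent, which is a different outcome from culture conversion.

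Neither document gives a lead time point, a testing order, a division of alpha, or a statement that either or both results are needed. The conjunction joining the two time points lists comparisons; it does not set a both-must-succeed rule.

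**The concern.** The success rule decides what the trial may conclude, and two readings of the plan lead to different trials.

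- If a significant result at either time point is enough, there are two chances to win at the full 0.05. The two-sided familywise error then exceeds the stated 5%, and the chance of a false claim for moxifloxacin exceeds the nominal 2.5% (though it stays below 5%).
- If both must be significant, error is controlled, but the chance of success is below the 80% in Protocol 9.1 unless the two results are perfectly correlated.

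Both results will presumably be reported. If they disagree, though, nothing says which one answers the primary objective, or which p-value counts among ordinary or corrected chi-square, Fisher's exact, regression and an HIV-stratified version. That choice could be made after the results are known. The trial is open label, and the SAP modification log shows that the list of tests was revised after trial initiation.

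**Working it through.** **1. Reproduce the plan's own figure.** Inputs from Protocol 9.1: 0.75 versus 0.60 (d = 0.15, mean 0.675), two-sided alpha 0.05, power 80%, continuity-corrected chi-square, 330 in total. SAP 2 gives 1:1 allocation.

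- Uncorrected: n0 = [1.95996·√(2·0.675·0.325) + 0.84162·√(0.75·0.25 + 0.60·0.40)]² / 0.15² = 151.87 per arm.
- Corrected: n = (n0/4)·[1 + √(1 + 4/(n0·d))]² = (151.87/4)·[1 + √(1 + 4/22.78)]² = 164.9, so 165 per arm and 330 in total.

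The figure is reproduced as one test of one contrast at the full 0.05. Nothing is reserved for a second time point. Exact power for that one test at 165 per arm is 80.4% (corrected), 80.5% (Fisher) and 83.5% (ordinary).

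**2. Assumptions on correlation.** The documents give no correlation and no separate rates per time point. I assume conversion is nested (whoever has converted by month 2 counts as converted at month 6). With control rates p2 and p6, the correlation is ρ = √[p2(1−p6) / ((1−p2)p6)]. For example, 60% and 80% give √(0.12/0.32) = 0.61.

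**3. Error if either may win.** No treatment effect, 165 per arm, 4,000,000 simulated trials per scenario, each test at two-sided 0.05:

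| Month 2 / month 6 | ρ | Two-sided, ordinary | Two-sided, corrected | For moxifloxacin, ordinary | For moxifloxacin, corrected |
|---|---|---|---|---|---|
| 60 / 80% | 0.61 | 8.68% | 6.60% | 4.32% | 3.28% |
| 60 / 90% | 0.41 | 9.42% | 6.53% | 4.71% | 3.26% |
| 60 / 95% | 0.28 | 9.38% | 6.16% | 4.69% | 3.08% |
| 40 / 60% | 0.67 | 8.42% | 6.52% | 4.20% | 3.25% |
| 50 / 60% | 0.82 | 7.95% | 6.18% | 3.97% | 3.09% |

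Fisher's exact test gives the corrected figures to two decimals. As a check, two independent tests give 1 − 0.95² = 9.75%. A bivariate normal calculation gives 9.1% at ρ = 0.5, 8.4% at 0.7 and 7.0% at 0.9.

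**4. Power if both must win.** Joint power is the bivariate normal probability that both statistics pass, taking each test alone at its planned power. For ρ from 0.28 to 0.82 it is 0.664-0.733 at 80% per test (corrected) and 0.709-0.769 at 83% per test (ordinary).

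**5. What a stated rule would do.** Under Hochberg, claim both if both p < 0.05; otherwise claim one if its p < 0.025. In the same simulations its two-sided error is 4.4-4.8% (ordinary), 3.1-3.5% (corrected) and 3.1-3.6% (Fisher). Power for one time point, over the same ρ range:

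| Test | Alone at 0.05 | Hochberg, both differ | Hochberg, only one differs |
|---|---|---|---|
| Corrected | 80% | 77.2-77.8% | 71.3-71.6% |
| Ordinary | 83% | 80.5-81.2% | 75.0-75.3% |

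**The case against.** The other side has several fair points.

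- **A test is named.** Protocol 9.2 names the chi-square, the regression is described as a means to precision, and Fisher's exact is a familiar fallback for sparse tables that behaves like the corrected chi-square here. This largely stands, so the choice of test is the smaller part of the problem. But SAP 6.3 gives no selection rule. Ordinary versus corrected moves the either-wins error from 6.2-6.6% to 8.0-9.4%, and the role of HIV stratification is open.
- **The inflation is modest and depends on one reading.** With the planned test it is 6.2-6.6%, and only if either result may win. True. Under the other reading the cost moves to power, so the gap matters either way.
- **The scenarios are assumed.** Three of the five put 60% at month 2, whereas a cure and completion figure fits month 6 better. The joint power assumes equal planned power at both time points, yet a 15-point gain is impossible from 90% or 95%. If the 60% and 75% held at both time points under nesting, the correlation would be 1, with no inflation and joint power still 80%. Missing cultures, or reading month 6 as status at that visit, would break the nesting. All of this stands: the figures are illustrations. The direction holds for any correlation short of 1.
- **Nothing shows that results had been seen.** Correct. None of the changes listed in the SAP log alters the time points or a success rule, and no such inference is drawn here.

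**Conclusion.** The concern holds. The plan tests one primary objective twice at the full 0.05, states no rule for combining the results, and is sized for one contrast that is not tied to either time point.

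Under an either-wins reading, two-sided error is 6.2-6.6% (corrected or Fisher) or 8.0-9.4% (ordinary). A false claim for moxifloxacin has probability 3.1-3.3% or 4.0-4.7%. Under a both-must-win reading, joint power is 66-73% (corrected) or 71-77% (ordinary). These ranges assume nested conversion, ρ between 0.28 and 0.82 and 165 evaluable patients per arm; the power figures also assume that each test alone has its planned power. The sample size arithmetic is correct. What is missing is the rule for deciding the primary objective, and it should be settled before the primary result is interpreted.

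**What to change.** In SAP 6.3, state one success rule that holds overall two-sided error at 0.05:

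- **(a) Fixed sequence:** name the lead time point and test the other only if the lead succeeds; or
- **(b) Hochberg**, as set out in the working.

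Requiring both results, or naming one time point primary and the other secondary, would also control error. The essential step is to choose one rule and write it down.

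Then:

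- Name the one test per time point whose p-value decides, and label the others supportive. The chi-square test, common to both documents, is a workable default. Say whether it is continuity-corrected, as in Protocol 9.1, and whether it is stratified by HIV status.
- In Protocol 9.1, say which time point the 60% and 75% refer to.
- In SAP 6.3, confirm that the first analysis time point is the scheduled Month 2 visit. Protocol 2.2 and SAP 1.2, 2 and 6.6 suggest this, while Protocol Table 1 (footnotes) and 7.2.3 let the intensive phase run longer for some patients.
- Record whether comparative results had been seen when the rule was adopted. If they had, report the rule as data-dependent.

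**Cost:** one paragraph in SAP 6.3, one sentence in Protocol 9.1 and that record; 330 patients still suffice. Under (a) the lead test keeps its full power, but the second time point can be claimed only with the joint power (66-73% corrected, 71-77% ordinary). Under (b) with the corrected test, power for one time point falls from 80% to 77-78%, or to 71-72% if only one time point differs. A plain 0.025 split would be dearer: 198 per arm, 396 in total, to keep 80% per time point with the corrected test.

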## 1.0 INTRODUCTION

### 1.1 Background

South Africa has the worst co-epidemic of tuberculosis (TB) and Human Immunodeficiency Virus (HIV) in the world where an estimated 70% of TB patients are co-infected with HIV. The dual epidemics have led to unacceptably high TB recurrence rates and previous TB treatment is a strong determinant of drug resistance. In 2010, patients with previously treated tuberculosis comprised 15% of global TB notifications. South Africa has the fourth highest number of multi-drug resistant TB (MDR TB) cases and the proportion of MDR TB was five times higher in those with previously treated TB. According to the World Health Organization (WHO), an estimated 53% of retreatment TB cases were co-infected with HIV in 2011 with only 54% of these patients receiving concomitant ART. In order to reduce the risk of recurrent TB, both the cure rate and the case detection rate need to be improved. In South Africa the treatment interruption rate on the standard WHO retreatment regimen is 12%. This non-adherence to the retreatment regimen likely contributes to the increasing burden of MDR TB. There is a critical need for an evidence-based retreatment regimen to improve treatment outcomes of recurrent TB, a regimen that can reduce morbidity and mortality in a shorter time period. The translation of these findings to the clinical setting is urgently required as it has the potential to change current retreatment protocols which are protracted with low success rates.

The existing World Health Organization Standardized Category II Retreatment Regimen (WSRR), adds a single injectable drug, streptomycin, to the first line 4 drug TB treatment regimen (RHZE) in the intensive phase. This regimen, used to treat 1 million patients each year, was based on expert opinion, and has yet to be tested in a randomized controlled clinical trial. Previous studies of the WSRR include a systematic review, a meta-analysis and a prospective cohort study. The systematic review, of published evidence of treatment of patients with a history of previous treatment or documented Isoniazid mono-resistance, included 33 trials, showed that in 1,907 patients lower failure, relapse, and drug resistance were associated with longer duration of Rifampicin, daily treatment and the use of a greater number of effective drugs.

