## **Withdrawal from the study**

Patients withdrawn from study due to a protocol violation will be included in the safety database of the study. Patients withdrawn from study because their initial TB isolate is found to be MDR –TB will not be followed up further, unless required for patient safety (e.g. an adverse event present, in which case follow-up should occur as clinically indicated). Similarly, patients withdrawn from study because their initial cultures are negative do not need to be followed up further (unless there is an ongoing adverse event). Participation in the study is strictly voluntary. A participant has the right to withdraw from the study at any time for any reason. Patients who withdraw their consent will not have to undergo any follow up procedures.

This study will be reviewed by a Safety Monitoring Committee (SMC) that meets for scheduled reviews of studies every year. A full SMC review will include an efficacy review and a futility review for detecting a survival difference. A full review will be scheduled at least annually after opening to accrual or on a frequency determined by the SMC. For each full review, summaries provided to the SMC will be broken down by treatment arm. Participants' baseline demographic and health characteristics will be summarized. Review of study conduct will address site accrual, premature study discontinuations and their reasons (administrative or loss to follow-up), tracking of potential losses to follow-up, data completeness. The SMC will also review participants' safety data, frequency and causes of death, as well as incidence of TB recurrence.

In addition, quarterly internal reviews of patient charts, SAE reports and regulatory submissions will be conducted.

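### The primary denominator is left open: SAP 5 lets the missing-data rule change with unspecified patterns, and SAP 6.3 neither scores loss before conversion nor requires a positive baseline culture

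*SAP*

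**What the plan says.** - SAP 5: "Missing data will be ignored (i.e. treated as missing at random) unless patterns are identified which would potentially bias analysis results". Data at a participant's non-missing time points are used.
- SAP 4: "All primary and most secondary analysis will be conducted based on the intention-to-treat (ITT) principle". The ITT population leaves out two groups: people found ineligible on pre-randomisation criteria, and "individuals with no post-randomisation visit and no data collected will be excluded". A participant seen once and then lost stays in.
- SAP 6.3: "culture conversion is defined as the first of two negative (or no growth) cultures at two different visits without an intervening positive culture". The proportion converted in each arm, at the end of the intensive phase and at month 6, is compared by chi-square or Fisher's exact test. No denominator is given, and there is no rule for death, withdrawal, loss, or one negative culture followed by loss. Protocol 9.2 adds nothing on this.
- SAP 6.7 (treatment failure and recurrence) counts participants who lack a negative culture at the end of treatment. Read literally, a missing result there is unfavourable.
- Protocol 9.1 plans 330 participants for "80% power to detect the difference between 75% of patients having culture conversion in the Intervention arm" and 60% in the control arm. It makes no allowance for loss.
- Protocol 4.1 admits patients on a positive smear and rifampicin susceptibility by GeneXpert, not on a positive culture. Under Withdrawal from the study, the protocol says that "patients withdrawn from study because their initial cultures are negative do not need to be followed up further" unless an adverse event is ongoing. The SAP does not say how these patients count.

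**The concern.** For a simple proportion, ignoring missing data removes a lost participant from the denominator, whereas counting everyone in the ITT set keeps that person in as not converted. Both readings fit the text. The exception in SAP 5 also permits a change of rule once patterns have been looked for, and because the trial is open label, missingness by arm is visible to those deciding. The primary comparison could then rest on a rule chosen after the data are known.

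The baseline-culture gap also concerns who belongs in the primary comparison. A participant who was culture-negative at entry has nothing to convert from, yet two later negatives satisfy the definition. Such participants pull both arms towards the same high rate.

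**Working it through.** **Inputs.** Rates of 75% and 60%, two-sided 0.05, 80% power and the continuity-corrected chi-square come from Protocol 9.1. The 1:1 allocation comes from SAP 2, so there are 165 per arm. Neither document gives a trial loss rate, so I assume 5% to 12%. The upper value borrows the 12% treatment interruption rate that Protocol 1.1 cites for the standard WHO retreatment regimen, which is only a proxy. Loss is unrelated to outcome throughout.

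**Step 1: the plan's own figure.**
Uncorrected n = [1.960√(2×0.675×0.325) + 0.842√(0.75×0.25 + 0.60×0.40)]² / 0.15² = 151.9 per arm.
Corrected n = (151.9/4)×[1 + √(1 + 4/(151.9×0.15))]² = 164.9, rounded up to 165 per arm or 330 in total. The plan's figure reproduces, with nothing left over for loss.

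**Step 2: power under each rule, if 75% and 60% are rates among observed participants.**
Power = Φ[(Δ − 1/n − 1.960·se₀)/se₁], where se₀ is the pooled and se₁ the unpooled standard error.
- No loss, n = 165: (0.150 − 0.0061 − 1.960×0.0516)/0.0509 = 0.84, power 80.0%.
- 12% loss, lost participants dropped, n = 145.2: (0.150 − 0.0069 − 1.960×0.0550)/0.0543 = 0.65, power 74.3%.
- 12% loss, lost participants not converted, 66.0% v 52.8%, n = 165: (0.132 − 0.0061 − 1.960×0.0541)/0.0536 = 0.37, power 64.5%.

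| Equal loss | Dropped (complete-case) | Counted as not converted |
|---|---|---|
| 5% | 77.8% | 73.6% |
| 10% | 75.3% | 67.1% |
| 12% | 74.3% | 64.5% |

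**Step 3: how often the rule matters.** Simulation of 1,000,000 trials, 165 per arm, binomial loss.

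| Loss | 75% v 60%: verdicts differ (uncorrected) | 60% v 60%: either rule significant, uncorrected | Same, continuity-corrected |
|---|---|---|---|
| 5% both arms | about 8% | 6.3% | 4.9% |
| 10% both arms | about 13% | 6.9% | 5.3% |
| 12% both arms | about 14% | 7.0% | 5.4% |
| 6% v 12% | not run | 12.6% | 10.2% |

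In the last row, counting losses as not converted rejects in 10.5% of trials by itself (uncorrected), against about 5% for complete-case.

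**Step 4: worked examples, 20 lost per arm (165 − 20 = 145).** Uncorrected p, with continuity-corrected p in brackets.
- 104/145 v 87/145 (71.7% v 60.0%): p = 0.035 (0.048). 104/165 v 87/165 (63.0% v 52.7%): p = 0.058 (0.075). The verdict changes.
- At about the planned effect, 109/145 v 87/145: p = 0.006 (0.008). 109/165 v 87/165: p = 0.014 (0.019). It does not change.

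With unequal loss (13 participants in one arm, 25 in the other) the verdict can move either way:
- 105/140 v 91/152, p = 0.006, becomes 105/165 v 91/165, p = 0.12.
- 114/152 v 91/140, p = 0.062, becomes 114/165 v 91/165, p = 0.009.

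**Step 5: culture-negative entrants kept as converters, no loss.** An assumed share of 5% turns 75% v 60% into 76.25% v 62.0% (0.95×75 + 5 and 0.95×60 + 5), a difference of 14.25 points and power of 76.8%. A share of 10% gives 77.5% v 64.0%, 13.5 points and 73.3%. Excluding them gives 77.8% and 75.3%.

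**The case against.** The best defence is that SAP 5 does state a default, and that an ITT set does not forbid analysing observed outcomes. That is fair, and a reader might infer an outright contradiction between SAP 4 and SAP 5 that the text does not contain. What remains is an ambiguity. The default does not settle whether someone lost after no or one negative culture is missing or has simply failed to meet the definition, and the exception allows a switch.

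A reader might also infer that the 5% error rate must be breached. The documents do not support that. SAP 6.3 does not say whether its chi-square test is corrected. With equal loss the corrected test stays at about 5% even if the favourable rule is deliberately picked, because that test is conservative to begin with.

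Nor do the figures show that counting losses as not converted is the right rule. It costs more power than complete-case, and when loss differs by arm it picks up the difference in loss as well as the difference in conversion.

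On baseline culture, it would be too strong to say that every culture-negative entrant will count as converted. The protocol foresees withdrawing these patients, so many may never supply two negatives, and GeneXpert at screening helps to confirm TB. The gap concerns those who stay in follow-up.

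SAP 6.1 already promises termination reasons and a CONSORT diagram. These will show losses but do not say how they are scored.

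**Conclusion.** The point stands as a should-fix. The documents allow two primary denominators and leave the choice open until after open-label data are seen. The result need not turn on it: with 20 lost per arm at the planned effect, both rules are significant. Under assumed equal loss of 5% to 12% they disagree in roughly one trial in twelve to one in seven. Inflation of the false-positive rate is small or absent at equal loss, depending on the test. It is clear (10% to 13%) in the assumed case of 6% v 12%, where most of it comes from one rule rather than from the choice between them.

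All of this rests on assumed loss rates and on loss unrelated to outcome. The 330 is not wrong for its stated inputs. Whether it is enough depends on whether the 75% and 60% already count losses as failures, which Protocol 9.1 does not say. The baseline-culture gap is separate and smaller: it dilutes the contrast and does not favour either arm.

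**What to change.** 1. **SAP 5 and 6.3.** Delete the exception for patterns. Before analysis, state one primary denominator and say how death, loss and withdrawal before conversion are scored at each of the two time points. Report the other rule and a tipping-point analysis as fixed sensitivity analyses, since neither rule is neutral when loss differs by arm.
2. **SAP 4 and 6.3.** Base the conversion analysis on randomised participants whose pre-treatment baseline culture was positive, and say how missing or contaminated baseline cultures count. Report the full ITT set as a sensitivity analysis. Reconcile this with the protocol's text on withdrawal for negative initial cultures.
3. **Protocol 9.1.** State whether the 75% and 60% already count losses as failures. If they do, 330 can stand, apart from the culture-negative exclusion (77.8% power at 5% excluded, 75.3% at 10%). If they do not, restate the power at 330 under the chosen rule, using the table in step 2.

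The cost is SAP wording, a few sensitivity analyses and a somewhat lower stated power. Baseline cultures are already scheduled, so no new data are needed. If losses count as not converted and the planning rates are among observed participants, holding 80% would take 191, 219 or 231 per arm at 5%, 10% or 12% loss. That exceeds the SAP's maximum of 330 in total, so restating the power is the practical course.
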